#### *Advisory Board and Expert Interview Qualitative Data*

After expert and advisory board interviews have taken place via Zoom, audio recordings will be stored on Shared File Areas in the Partners Network. Audio recordings will be directly uploaded into NVIVO and sent securely to study staff at the University of Utah for analysis.

#### *Intervention Arm Components*

Of the approximately 80 participants recruited for Phase 2 of the study, 40 will be randomized to enhanced usual care, and 40 will be randomized to the health insurance navigation intervention. As described above, the intervention arm will involve 4 sessions delivered by a navigator.

#### *Intervention Fidelity*

The patient navigator (PN) will undergo training by the Co-investigators and pilot sessions. The NCI, with support from the ACS, established the Patient Navigation Research Program (PNRP) to implement and evaluate patient navigator programs. The PNRP developed a navigation performance checklist with 3 quality indicators of care: 1) participant interaction (e.g., established rapport), 2) care management (assessed subjects' understanding), and 3) intervention delivery (e.g., relevant information provided on insurance options, cost savings). Study investigators will review 15% of patient navigation encounters using these quality indicator criteria.

## Assessments

### Phase 1 Assessments

During the Open Pilot of the intervention, participants will complete a baseline survey and a 3-month post-program follow up survey. Participants will be remunerated \$20 for the completion of each survey by the University of Utah. LTFU extracted medical record data will provide information on cancer diagnosis, age at diagnosis, years since diagnosis, and type of treatment. The open pilot will also involve an exit interview, which is described in further detail below.

### Phase 2 Assessments

During the pilot trial, participants will complete a baseline survey, a 3-month post-program follow up survey. LTFU extracted medical record data will provide information on cancer diagnosis, age at diagnosis, years since diagnosis, and type of treatment.

### Phase 3 Assessments

After the completion of the follow-up survey, investigators will conduct In-depth exit interviews with the 40 intervention arm participants to assess participants' 1) satisfaction with the intervention, 2) recommendations for modifications on overall session topics and intervention content (e.g., physician communication, cost management strategies) and 3) recommendations for modifications on delivery modality (e.g., number and length of sessions, videoconferencing delivery) . Participants will be remunerated \$20 for their time by the University of Utah.

## **VI. BIOSTATISTICAL ANALYSIS**

### Analysis Plan

#### Qualitative Data

For qualitative analyses of participant focus groups advisory board meetings, individual expert interviews, and exit interviews, all data will be analyzed by MGH and University of Utah study staff using NVivo qualitative software. For qualitative analysis of advisory board and individual expert interviews, audio files will be uploaded into NVIVO software and analyzed using a Rapid Analysis method. Content analyses for the participant focus groups an exit interviews will be conducted including a structural thematic framework, categories, and coding plan. For focus group data, a coding framework will be developed. To ensure coding reliability, coding discrepancies will be resolved through

discussion and comparison of raw data. Coding will continue until a high level of reliability (Kappa=  $\geq 0.80$ ) is established. Co-investigators will provide an expert review of the results.

**Focus Group Data:** A coding framework will be developed for themes and codes according to participants' feedback 1) barriers to accessing and using health insurance 2) resources to support health insurance access and use, 3) navigation program content4) intervention structure and dose, 5) program delivery, 6) program acceptability, 7) aspects of coverage that are not well understood

**Advisory Board and Individual Interview Data:** A coding framework will be developed for themes and codes according to the advisory board feedback on 1) barriers, 2) resources, 3) content, 4) intervention structure and dose, 5) delivery and 6) selection criteria

**Exit Interview Data:** A coding framework will be developed for themes and codes according to participants' feedback on 1) satisfaction with the intervention, 2) recommendations for modifications on overall session topics and intervention content (e.g., physician communication, cost management strategies). and 3) recommendations for modifications on delivery modality (e.g., number and length of sessions, videoconferencing delivery)

#### **Quantitative Data**

For quantitative data, [name] team at HCI will conduct the analyses with input from [name] and her study team, and the LTFU study team. As discussed in Participants, we will sample by Medicaid expansion vs. non-expansion states. All analyses will be weighted using inverse sampling probabilities so that results are representative of the overall LTFU study cohort.

At baseline, all pilot participants will complete a baseline. The HINP navigator will use each participant's baseline survey responses to personalize and individualize sessions. At the 3-month post-program follow-up, participants will complete the Phase 1 survey Outcome questions, which will be asked within the 5-month time frame period after trial enrollment. Participants will also be asked questions below about feasibility and acceptability.

We will use descriptive statistics to report on the following endpoints: intervention feasibility (percent of participants enrolled), acceptability (satisfaction, perceived support) and efficacy (e.g., ACA familiarity, health insurance literacy, intention to adhere to recommended survivorship care, provider communication, and coverage status).

Descriptive statistics will examine group differences at baseline; any imbalances will be adjusted. We will use chi square and independent t-tests to compare end-of-intervention changes in preliminary efficacy outcomes between the two groups. Although a 3-month post intervention follow-up period is brief, we will also conduct exploratory comparisons with other study outcomes to see if trends change in the expected direction. We will compare pre/end-of-treatment, within groups, with paired t-tests. In addition, we will use bivariate statistics to examine sociodemographic and cancer-related factors (type of

diagnosis, age at diagnosis, years since diagnosis, cancer treatment, chronic conditions, cancer treatment (e.g., cranial radiation yes/no, anthracycline exposure yes/no) associated with feasibility, acceptability and preliminary efficacy outcomes.

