***Childhood Survivors are a growing population in need of medical surveillance.***

Children diagnosed with cancer have experienced improved survival rates over time, with more than three-fourths becoming long-term survivors. However, survivors of childhood cancer often face new and continued health care challenges and require ongoing care to monitor and treat long-term effects of their cancer and treatment throughout adulthood. Ongoing medical treatment and surveillance, with access to quality healthcare and coverage, are critical.

***Although quality health insurance coverage is critical to this population, it has been complex to obtain.*** Given their ongoing health care needs, obtaining and navigating health insurance coverage is vital to ensure access to needed survivorship care. However, this can be difficult for individuals with pre-existing conditions such as a cancer diagnosis, who have historically faced denials of coverage, steep premiums, or “job lock” that keeps them from changing jobs for fear of losing coverage. At the same time, childhood survivors have had higher rates of uninsurance, unmet health care needs, and burdensome costs. These survivors are also less likely than siblings to be employed, married, and have a higher household income. [name] found that childhood survivors and siblings had similar rates of coverage, yet they differed by types of coverage and experiences obtaining coverage. Uninsured survivors in particular were more likely to experience financial burdens from medical care that affected their care utilization.

***Health care reform offers opportunities for childhood survivors to obtain quality coverage.*** The ACA was signed into law in 2010 and is intended to increase access to affordable, quality health care. ACA policies offer considerable opportunities for populations with pre-existing conditions like childhood survivors to obtain coverage and improve access to needed care. [name] and colleagues delineated the implications of specific ACA provisions for insurance coverage for childhood survivors.

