***Recent study team reports of childhood survivors' underinsurance and its effects on financial burden and health care utilization.*** [name] led analyses describing patterns of health insurance coverage and care accessibility and affordability in an NHIS sample of adult childhood cancer survivors compared to adults without cancer during 2010-2014. Significantly more childhood survivors reported being uninsured, delaying medical care (24.7% vs 13.0%), needing but not getting medical care (20.0% vs 10.0%), and having trouble paying medical bills (40.3% vs 19.7%), compared to controls (ps<0.0001). In 2017, [name] and the study team published findings in *JAMA Internal Medicine* and *JCO* documenting that, compared to siblings, childhood survivors were significantly more likely to endorse indications of being underinsured, including being 84% more likely to borrow money because of medical expenses, 80% more likely to worry about being unable to pay for a needed treatment, and 74% more likely to worry they wouldn't be able to afford to fill a prescription. In addition, childhood survivors were more likely to report spending a higher percentage of their income on out-of-pocket medical costs. Survivors reported spending almost more than \$1000 annual out-of-pocket costs compared to siblings. A higher percentage of income spent on out-of-pocket medical costs was significantly associated with survivors' problems paying medical bills (OR, 8.9; 95% CI, 4.4 to 18.0); deferring care for a medical problem (OR, 3.0; 95% CI, 1.6 to 5.9); skipping a test, treatment, or follow-up (OR, 2.1; 95% CI, 1.1 to 4.0); and thoughts of filing for bankruptcy (OR, 6.6; 95% CI, 3.0 to 14.3).

***Intervention and program development with childhood cancer survivors.*** [name] has studied the health behaviors and perceptions of childhood cancer survivors.

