### **c. Rationale of Proposed Research**

Health care reform under the Patient Protection and Affordable Care Act (ACA) offers considerable opportunities for childhood cancer survivors to obtain coverage and improve access to needed care. However, in the general population, many people have low understanding of available insurance benefits and resources, and have limited health insurance literacy (i.e. perceived knowledge, ability, and confidence to make informed decisions about choosing and using health insurance). Misperceptions about which services require out-of-pocket costs may lead some enrollees to avoid services that are in fact exempt from cost sharing. Even with coverage protections from the ACA, barriers to obtaining quality coverage (e.g., in states without Medicaid expansion) and accessing needed care may remain for childhood survivors. Understanding and navigating insurance benefits is crucial for cancer survivors to obtain the health care they need. In this new post-reform landscape, the degree to which coverage and costs have changed for childhood cancer survivors is still largely unknown.

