### III. SUBJECT SELECTION

#### Participants: Inclusion and Exclusion Criteria

LTFU study staff at St. Jude Children's Research Hospital keep updated participant contact records for this study, which allows for participants to be approached for additional research studies. For Phases 1 and 2, the LTFU study staff will recruit a total of approximately 122 participants from the Long-Term Follow-Up Study cohort.

Phase 1 will involve recruitment of 32 participants for four focus groups and approximately 5-10 participants for the open pilot. Phase 1 participants will not be eligible for Phase 2 participation. For the focus group activities of this Phase, participants will be randomly selected stratified according to whether they reside in a state with or without Medicaid expansion, which LFTU staff will determine based on participant addresses available from the LTFU data records.

Phase 2 will involve recruitment of 80 randomly-selected participants for the pilot randomized trial. Participants will be randomly selected stratified according to whether they reside in a state with or without Medicaid expansion, which LFTU staff will determine based on participant addresses available from the LTFU data records.

Phase 3 participants will be recruited from the Intervention Arm of Phase 2 (approximately n=40).

For both Phases, we will exclude participants who : (1) do not have health insurance, (2) are under the age of 18, (3) are unable to give informed consent due to psychiatric or cognitive impairment as determined in consultation with study PI, patient navigator, or oncology social worker, and (4) do not have access to a smartphone, computer or tablet with internet access. Importantly, we will closely document and monitor the

numbers of individuals who are unable to participate given this final criterion, as it will further inform the feasibility of this intervention modality.

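### Weights built on one binary stratum cannot make results representative of the overall LTFU cohort; the claim should be narrowed to the population the design can reach

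*Combined protocol and SAP*

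**What the plan says.** Section VI, Quantitative Data, sets the rule and its purpose: "All analyses will be weighted using inverse sampling probabilities so that results are representative of the overall LTFU study cohort". The sentence before it ties the sampling to expansion versus non-expansion states. Section III (Inclusion and Exclusion Criteria) and Section IV (Intervention Assignment and Randomization) describe the same two strata. The table in Section V labels the stratum by Medicaid rather than by state expansion status, but under either label it is a single binary variable.

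Section IV draws from each stratum until 80 people have consented, then randomises 40 to each arm. People who decline are replaced by further draws.

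Section III excludes, besides minors, those who "do not have health insurance", those who "are unable to give informed consent due to psychiatric or cognitive impairment" and those who "do not have access to a smartphone, computer or tablet with internet access". The last group will be counted, as feasibility information. No such count is planned for the uninsured.

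Sources of Subjects and Recruitment Methods describes 21,841 living members with contact details as eligible, which is the number before those exclusions.

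The documents describe no non-response weight, no calibration to cohort characteristics and no attrition weight. They give neither the stratum sizes nor the split of the 80 across strata. On testing, Quantitative Data says "We will use chi square and independent t-tests to compare end-of-intervention changes in preliminary efficacy outcomes between the two groups", without saying how weighted versions of these tests would obtain their standard errors.

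**The concern.** Inverse-probability weighting represents a population only if everyone in it had some chance of inclusion and the weight reflects that chance. Both conditions fail here for the population named. The exclusions give some members no chance, and the chance of enrolling among the rest depends on consent, which the weight ignores.

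The missing group is close to the trial's subject. The background section reports: "Uninsured survivors in particular were more likely to experience financial burdens from medical care that affected their care utilization". Financial distress related to medical costs is one of the measured outcomes, and Quantitative Data plans descriptive reporting alongside the tests. Weighted levels from insured, connected volunteers would therefore be presented as cohort figures, and someone planning the next trial could use them as such.

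**Working it through.** **Inputs from the documents.** Frame 21,841; enrolled 80 (40 per arm); two strata; weights by inverse sampling probability. The documents state no figure that depends on the weighting claim, so there is none to reproduce. Stratum shares, consent rates, excluded shares and trait prevalences below are assumptions.

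**Step 1. What the weight can change.** With N_h members and n_h enrolled in stratum h, the weight is w_h = N_h / n_h. On average this is 21,841 / 80 = 273, a sampling fraction of 80 / 21,841 = 0.37%. The weighted mean is the sum over h of W_h × (mean of those enrolled in h), where W_h = N_h / N. Everyone in a stratum has the same weight, so the weights change only how much each stratum contributes. They do not change who within a stratum was enrolled.

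**Step 2. Illustration.** Assume 40 enrolled per stratum, an expansion share of 70%, and a trait held by 10% of members in expansion states and 20% elsewhere. The true level is 0.7 × 10 + 0.3 × 20 = 13.0%.

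| Enrolment with trait / without | Enrolled level, expansion | Enrolled level, non-expansion | Weighted | Error (points) |
|---|---|---|---|---|
| 30% / 30% | 10.0% | 20.0% | 13.0% | 0 |
| 20% / 30% | 0.02/0.29 = 6.9% | 0.04/0.28 = 14.3% | 9.1% | −3.9 |
| 0% / 30% (excluded by design) | 0% | 0% | 0% | −13.0 |

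In the first row the unweighted level would be 15.0%, so the weights do correct the stratum mix. They do not repair selective consent (second row) or exclusion (third row). For expansion shares from 50% to 80%, the second-row error runs from −4.4 to −3.6 points and the third-row error from −15 to −12 points.

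**Step 3. Effect on an outcome level.** Let u be the excluded share and D the excluded-minus-included difference. The cohort level then exceeds the included level by u × D:

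- 0.05 × 10 = 0.5 points
- 0.10 × 20 = 2.0 points
- 0.15 × 30 = 4.5 points

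Previous Studies reports 40.3% of childhood survivors with trouble paying medical bills. If that were the true level, the included group would show 39.8%, 38.3% or 35.8%. The figure comes from a national survey sample of 2010–2014, not from this cohort or the trial's own measure, so it only fixes a scale.

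**Step 4. Against sampling error.** At a level of 40%, the unweighted 95% half-width is 1.96 × √(0.4 × 0.6 / 80) = 10.7 points for all 80, and 1.96 × √(0.4 × 0.6 / 40) = 15.2 points for one arm. The Step 3 range lies below both.

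**The case against.** **The consequence is small.** This is a pilot whose sample size rests on feasibility and exploration, and no stated power, alpha or N depends on the sentence. Under the assumptions in Step 3 the error is smaller than the sampling error. This stands as a limit on importance. It does not make the claim true: a wider interval around a level in the wrong population is still an interval for that population.

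**The restriction is already visible.** Section III lists the exclusions, and Secondary Outcomes limits insurance status to people insured at enrolment. These passages soften the claim, but neither narrows the stated target. The promise to adjust for imbalances concerns baseline differences between arms, so it does not help.

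**The frame and the eligible group differ, but only to second order.** The rationale says that "barriers to obtaining quality coverage (e.g., in states without Medicaid expansion) and accessing needed care may remain for childhood survivors", so eligibility could differ by stratum. With an assumed 60% expansion share and 95% eligible there, against 90%, 85% or 80% elsewhere, the eligible expansion share is 0.57/0.93 = 61.3%, 0.57/0.91 = 62.6% or 0.57/0.89 = 64.0%. Those are shifts of 1.3 to 4.0 points. Multiplied by an assumed 10 to 20 point outcome difference between strata, the effect is about 0.1 to 0.8 points. That is too small to justify a weight built on estimated eligible fractions, so stating the assumption is enough.

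**The tests.** A reader might infer that the weighted chi-square and t-tests will reject too often. The documents do not support that. It would need disproportionate sampling of the strata, ordinary rather than design-based standard errors, and similar stratum variances; none of these is stated. Silence about standard errors is missing detail, not evidence of a wrong method.

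**Conclusion.** The claim of representativeness is wrong as written, and the conclusion rests on the documents alone. The weights depend on one binary variable, some members have no chance of enrolment, and consent within a stratum is not modelled. At most the weights restore the Medicaid-expansion mix among eligible, contactable members.

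The size of the resulting error cannot be estimated, because the documents give no excluded share, consent rate or stratum count. The 0.5 to 4.5 points above are conditional on assumed inputs and should not be read as an estimate for this cohort.

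A reader might also infer that the comparison between arms is biased. It is not, by this alone: randomisation takes place among those who enrol, so the comparison is internally valid for them. Carrying it over to the excluded would fail only if the intervention worked differently in them, and the documents give no evidence on that. What is overstated is generalisability, chiefly of descriptive levels. The wording should be corrected; the design need not change.

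**What to change.** Replace the clause on representativeness with:

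> Weighted estimates standardise results to the Medicaid-expansion/non-expansion mix of contactable adult LTFU members who are insured, internet-connected and able to consent, assuming eligibility and follow-up completion are similar across strata; they do not represent excluded, non-consenting or lost-to-follow-up members.

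In addition:

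- Report the number excluded for lack of insurance, by stratum, beside the no-device count already planned in Section III.
- Report the unweighted, stratum-adjusted between-arm contrast alongside the weighted one.
- Leave raw enrolment and session counts unweighted.
- If weighted tests are kept, use design-based standard errors (sandwich for means, Rao–Scott for chi-square). This is a secondary precaution that matters only if the strata are sampled disproportionately.

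The cost is a narrower generalisability statement, one extra screening count and slightly more analysis work. Recruitment, intervention and sample size are unchanged.

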### **Aim 2: To conduct a videoconferencing-based pilot randomized trial of the HINP (n= approximately 80).**

A2a: To assess the feasibility (number of eligibles enrolled and sessions completed) and acceptability (satisfaction, perceived support) of participants undergoing the HINP.

A2b: At 3-month post-program follow-up, to assess the efficacy of the HINP to assist participants with accessing and utilizing coverage and managing costs. Primary

outcomes are 1) health insurance literacy and 2) financial distress related to medical costs

**A2b Hypothesis:** The HINP, compared to enhanced usual care, will improve participants' health insurance literacy and decrease financial distress.

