### Participant Characteristic Measures (see study surveys)

Characteristics: Age, Gender, Education, Race/Ethnicity, Partnership/Marital Status

Enabling Characteristics: State of Residence, Familiarity with ACA Policies

Health Insurance Literacy: Confidence in Understanding of Terms (e.g. Coinsurance), Confidence in Choosing, Comparing, and Using Insurance, Household and Personal Income

Need: Cancer Diagnosis, Age at Diagnosis, Years Since Diagnosis, Treatment Type, Recurrence of Primary Cancer, Second Malignancy, Other Chronic Conditions.

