### Outcome Measures

Insurance Coverage: Insurance Status, Difficulty or Denial in Obtaining Coverage due to Health History (within past 2 years), Difficulty Finding and Choosing a Plan

Underinsurance: Not Taking a New Job in Order to Keep Health Insurance, Difficulty Finding a Provider who Accepts Insurance/ Not Able to Obtain an Appointment as Needed, Unmet Healthcare Need Due to Cost, Provider Visits in Past Year, or Out of Pocket Healthcare Costs, Out of Pocket Healthcare Costs/Premium Costs, Problems Due to Medical Expenses, Worry Related to Medical Costs

Coverage-Related Variables: Current Coverage and Coverage History

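### Continuous efficacy outcomes are compared by t-tests without covariates, with adjustment only if imbalance is seen; a pre-specified baseline-adjusted model would usually be more precise at no cost

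*Combined protocol and SAP*

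**What the plan says.** The between-arm analysis of efficacy is one sentence in section VI, Quantitative Data: "We will use chi square and independent t-tests to compare end-of-intervention changes in preliminary efficacy outcomes between the two groups". The covariate rule precedes it: "Descriptive statistics will examine group differences at baseline; any imbalances will be adjusted". The within-arm analysis follows: "We will compare pre/end-of-treatment, within groups, with paired t-tests". A general rule covers all of these: "All analyses will be weighted using inverse sampling probabilities so that results are representative of the overall LTFU study cohort". No baseline-adjusted comparison of the arms appears elsewhere. The bivariate analyses planned in the same section relate sociodemographic and cancer factors to outcome; they do not estimate the treatment effect.

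The hypothesis being tested is in Aim 2 (A2b): "The HINP, compared to enhanced usual care, will improve participants' health insurance literacy and decrease financial distress". Aim 2 calls these two outcomes primary; the Outcomes part of section VI lists them as secondary. Pilot Trial Design gives about 40 per arm, justified by feasibility, acceptability and exploring differences in outcomes. It states no power, effect size, SD or correlation.

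The data for a baseline-adjusted analysis are already scheduled (Phase 2 Assessments): "During the pilot trial, participants will complete a baseline survey, a 3-month post-program follow up survey".

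Scoring is not given. The measures lists name item topics only, for example "Confidence in Choosing, Comparing, and Using Insurance" for literacy and "Problems Due to Medical Expenses, Worry Related to Medical Costs" among the cost items.

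**The concern.** There are two separate weaknesses.

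**Precision.** A t-test on change scores fixes the slope on baseline at 1, and a t-test on follow-up scores fixes it at 0. ANCOVA estimates the slope, so in large samples it is never less precise than either. With about 40 per arm the interval for the arm difference is wide, and the baseline score can narrow it without another participant or visit.

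**A model chosen after the data are seen.** The adjustment rule leaves open which variables are examined, what counts as an imbalance and what model follows. Chance imbalance is also a poor trigger. The gain comes from the baseline score predicting the follow-up score, and it is there whether or not the arms look balanced.

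At stake is the estimate a reader would use to judge whether the programme moved literacy or financial distress. The validity of the randomised comparison is not in question.

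**Working it through.** **Inputs from the documents.** About 40 per arm, 1:1 (Pilot Trial Design; Intervention Assignment and Randomization). Two surveys, at baseline and 3 months post-program. There is no survey at the end of the sessions, so the planned comparison has to use the 3-month score.

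**Assumed, because the documents give none.** Correlation ρ between baseline and follow-up of 0.3 to 0.9; unit SD at both times; two-sided 95% intervals; full follow-up, with 32 per arm as a check. There is no power calculation in the plan to reproduce.

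**Formulas.** The half-width is t × √(2V/n), where V is the variance per participant:

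- change score: V = 2(1 − ρ), 2n − 2 df
- follow-up score only: V = 1, 2n − 2 df
- ANCOVA: V = (1 − ρ²) × [1 + 1/(2n − 4)], 2n − 3 df; the bracket allows for chance baseline imbalance and is 77/76 = 1.013 at n = 40

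Ignoring the bracket, the ratio of ANCOVA variance to change-score variance is (1 − ρ²)/[2(1 − ρ)] = (1 + ρ)/2, and to follow-up-score variance it is 1 − ρ².

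**Worked case, n = 40, ρ = 0.5.** Change score: 1.991 × √(2 × 1/40) = 0.445. ANCOVA: 1.991 × √(2 × 0.75 × 1.013/40) = 0.388. Reduction: 1 − 0.388/0.445 = 12.8%.

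| ρ | Half-width, change | Half-width, follow-up | Half-width, ANCOVA | Reduction v change | Reduction v follow-up |
|---|---|---|---|---|---|
| 0.3 | 0.527 | 0.445 | 0.428 | 18.8% | 4.0% |
| 0.5 | 0.445 | 0.445 | 0.388 | 12.8% | 12.8% |
| 0.7 | 0.345 | 0.445 | 0.320 | 7.2% | 28.1% |
| 0.9 | 0.199 | 0.445 | 0.195 | 1.9% | 56.1% |

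With 32 per arm every reduction is within 0.2 points of these. The two readings of *changes* behave in opposite ways: against change scores the gain shrinks as ρ rises, and against follow-up scores it grows. The change-score reading is the more natural one.

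**In terms of power.** For an assumed difference of 0.5 SD at ρ = 0.5 and two-sided 0.05, power with 40 per arm rises from 61% to 73% (60% and 72% in simulation). ANCOVA with 30 per arm matches the change-score test with 40.

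**Unequal SDs, change-score reading, n = 40.** With follow-up SD 0.8 times baseline SD, the reductions at the four values of ρ are 28.7%, 23.9%, 20.2% and 21.5%. With 1.25 times, they are 10.8%, 4.9%, 0.3% and 1.9%; at ρ = 0.75 and 0.8 ANCOVA is wider by 0.4% and 0.7%.

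**With the planned weights.** Simulation used 2,500 trials per setting, a 50:50 sample by Medicaid-expansion stratum, cohort shares from 50:50 to 80:20, weighted least squares and HC2 robust standard errors. Mean reductions against the change score were 18.7–19.0%, 12.6–12.9%, 7.1–7.3% and 1.8–2.1%; coverage was 93–96%. Single trials vary: at 65:35 and 40 per arm, the ANCOVA interval was the narrower in 99.8%, 98.4%, 93.5% and 70.5% of trials.

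**How often the imbalance rule would act on the baseline score.** Taking imbalance as baseline p < 0.05, in 5% of trials; as a standardised difference above 0.2, in 37% (40 per arm, 200,000 draws). These are chances of triggering extra adjustment. A change-score analysis uses the baseline score in every trial, at a fixed slope of 1.

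**The case against.** The strongest objection is about timing. Methods of Enrollment lists randomisation before participant details are passed on, and the section V table has the receiving team collect the baseline survey afterwards. Baseline self-ratings might therefore be given by people who know their arm, whereas the calculation treats baseline as independent of arm. This stands as a gap in the plan. It does not favour the t-test, because a change score uses the same baseline value.

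Second, few outcomes may qualify. The plan also provides chi-square tests, insurance status is categorical, the provider-discussion items are yes/no, and some cost items could be binary. Scoring may be set out in the surveys the protocol refers to, which were not available here. The algebra is certain; its reach is not.

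Third, the gain is not universal. If change scores are meant, part of the benefit of baseline is already taken, and the larger figures for follow-up scores do not apply. With a larger SD at follow-up the gain can be nil, although the worst loss found at 40 per arm is under 1% of interval width.

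Last, this is a pilot. The Outcomes section makes feasibility and acceptability primary and states no power for efficacy, so a valid but less efficient test could be seen as a minor matter. Against that, Aim 2 sets a directional between-arm hypothesis and labels the same two outcomes primary.

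**Conclusion.** The concern holds. The planned comparison is valid, but for continuous scales it is usually less precise than a baseline-adjusted model, and the adjustment rule is too loose to fix the analysis in advance. With 40 per arm and equal SDs, the interval would narrow by about 2% to 19% against change scores, or 4% to 56% against follow-up scores, for correlations of 0.3 to 0.9. The planned weights do not alter the mean gain materially. These sizes rest on an assumed correlation, on the ratio of follow-up to baseline SD and on continuous scoring, none of which the documents state. The case for pre-specification does not depend on them. The change should be made, but the trial is not invalid without it.

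**What to change.** For each efficacy outcome scored as a continuous scale, replace the between-arm t-test and the imbalance rule with one pre-specified model:

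- 3-month post-program score = arm + baseline score, optionally + Medicaid-expansion stratum
- the planned inverse-sampling-probability weights, with robust standard errors
- the adjusted arm difference reported with its 95% confidence interval

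List which outcomes are scored as continuous. State whether the baseline survey is completed before the participant learns the allocation. Reporting the observed baseline to follow-up correlation would help in sizing a later trial. Categorical outcomes, the within-arm paired tests and the allocation method are not affected.

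The cost is analysis-plan wording and one degree of freedom, about 1.3% in variance at 80 participants and already counted in the interval widths above. No extra data, visits or participants are needed.
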